7. STATISTICAL METHODS

Statistical Analysis Plan (SAP)

There will be a formal SAP, separate from this HPI CARE Trial protocol. The formal SAP will be completed prior to database lock and the analysis of any HPI CARE Trial endpoints data. The SAP will detail the planned statistical analyses. The subsections below summarize the planned analyses.

Primary Effectiveness Endpoint

The primary objective of this trial is to determine whether the use of the Acumen™ HPI Feature Software to guide hemodynamic management in critically ill patients in the cardiac operating room (OR) and the cardiovascular intensive care unit (CVICU) reduces the duration (t[mins]) of hypotension below a threshold of Mean Arterial Pressure (MAP), defined as MAP <65mmHg.

Sample Size Justification

In the HPI CARE Trial, the reduction of the mean duration of hypotension in the operating room (OR) and intensive care unit (ICU), is the primary endpoint. The following statistical hypotheses are designed and used for the sample size estimation.

$$H_n: \mu_1 \geq \mu_0$$

$$H_a: \mu_1 < \mu_0$$

where μ_1, μ_0 are the mean hypotension duration of the test arm and reference arm, respectively.

Because there are no publications available targeting hypotension management in the ICU, the sample size estimation is conducted based on the summary statistics from OR measurement. By the summary statistics (mean and standard deviation) of hypotension duration from post-CPB and closed chest ^[3,5], the following statistics are calculated and applied in sample size estimation: hypotension mean=29 (minutes), standard deviation=29.4 (minutes).

By clinical study design, type I error $\alpha = 0.025$ (one side test), test power= $(1 - \beta) = 0.80$, the expected hypotension duration reduction rate by HPI software and the treatment protocol is 30%, the expected ratio of hypotension duration standard deviation divided by the mean hypotension in the test arm will be 1.10 (obtained from a previous non-cardiac OR HPI study, Edwards Lifesciences), with SAS PROC POWER, the estimate of sample size is 171 per group. β is type II error.

Primary Safety Endpoint

The primary safety endpoint is to assess all serious intraoperative and post-operative adverse events through 30 days, including serious device-related events.

Analysis Populations

A. mITT population

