All the other statistical methodology used in sensitivity analysis, safety analysis, and exploratory analysis will be detailed in the SAP.

Note: In this study, the sample size is not big enough to ignore the approximate property with Z score test, especially in the interim analysis.

Planned Interim Analyses

To monitor the effectiveness and safety of HPI software on hypotension management in cardiac surgery and ICU, one interim analysis is planned and will be conducted at the time that half of the enrolled study subjects complete surgery and the hemodynamic measurements are downloaded from the monitoring platform.

To compensate for the early look at the data during the interim analysis, using the Pocock methodology, for this study design, 11% extra study subjects will be enrolled. Considering drop-out through ICF withdrawal, subjects lost to follow-up, and roll-in subjects for training, another 10% attrition is added for subject enrollment; the final sample size is 175 subjects per group.

Secondary Endpoints

The following secondary endpoints will be analyzed per the SAP:

- TWA of MAP < 65 mmHg in the OR Period (T1)
- TWA of MAP < 65 mmHg in the CVICU Period (T2)
- TWA of MAP < 65 mmHg in the CVICU Period, pre extubation (T3)
- TWA of MAP < 65 mmHg in the CVICU Period, post extubation (T4)
- Mean duration in minutes of MAP < 65 mmHg in the time periods of T1, T2, T3 and T4
- Mean duration in minutes of MAP < 60 mmHg in the time periods of T1, T2, T3 and T4
- Mean duration in minutes of MAP < 55 mmHg in the time periods of T1, T2, T3 and T4
- Mean duration in minutes of MAP < 50 mmHg in the time periods of T1, T2, T3 and T4

Clinical endpoints:

- Acute kidney injury (AKI)⁷, as defined by the modified KDIGO criteria, stages 1, 2 and 3.
- Neurocognitive deficit, as evaluated by the MMSE, CAM-ICU 7, and bCAM assessments.
- Periprocedural Myocardial injury, measured with high-sensitivity Troponin I and as defined a threshold of 70 times the upper reference limit⁶. or >1400 pg/ml

THIS DOCUMENT CONTAINS CONFIDENTIAL AND PROPRIETARY INFORMATION OF EDWARDS LIFESCIENCES, LLC. IT MAY NOT BE REPRODUCED OR DISCLOSED WITHOUT PRIOR WRITTEN PERMISSION FROM EDWARDS LIFESCIENCES, LLC.

Edwards Lifesciences, Edwards, the stylized E logo, HemoSphere, Acumen IQ, Swan Ganz and ForeSight Elite are trademarks of Edwards Lifesciences Corporation.

Additional Evaluations

The following additional evaluations will be included and are considered exploratory:

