2.4.2. Experiment Design Parameter

 Edwards	Revision Date: May 7, 2024	Rev	For Use Only by Affiliates of Edwards Lifesciences	Page 8
	Title	A randomized trial of the Hypotension Prediction Index in the cardiac operating room and the intensive care unit		

It is frequently encountered upon intensive care unit (ICU) admission, where patients become hypotensive in the immediate post-operative period, shortly after the arrival from the operating room (OR). Hypotension upon anesthesia-to-ICU drop-off is more frequent than previously reported and may be associated with adverse clinical outcomes^[9]. Many studies have been conducted exploring the risks of intraoperative hypotension during non-cardiac surgery, also there are literatures focusing on the hemodynamic management in operating room during cardiac surgery, but up to now, no valid evidence available from hemodynamic management operation for the patients discharged to ICU could be applied in sample size simulation for HPI CARE study. The association between the severity and duration of intraoperative hypotension and postoperative stroke in patients undergoing cardiac surgery was evaluated in a retrospective cohort study of 7,457 consecutive adult patients who underwent cardiac surgery with the aid of cardiac pulmonary bypass^[9]. From this study, following summary statistics (table 1) are drawn that will be integrated in sample size simulation for HPI CARE study. Recently, a single medical center prospective cohort feasibility clinical study is designed and executed to evaluate the use of the HPI in cardiac surgeries requiring cardiopulmonary bypass (CPB) ^[13]. Totally 37 subjects were enrolled for this study. By 33 valid subjects, the mean total intraoperative hypotension duration is 9 minutes, and the corresponding stand deviation is 15 (minutes) for close chest period in whole cardiac surgery procedure, which will be integrated together with the summary statistics from post cardiac pulmonary bypass (see table 1) in the sample size simulation.

Table 1: Summary Statistics of intraoperative hypotension during post-Cardiac Pulmonary bypass period^[9]

MAP(mmHg)	Stroke (n=111) Mean±STD (minutes)	No Stroke (n=7346) Mean±STD (minutes)	All Patients (n=7457) Mean±STD (minutes)
<55	9.2±20.00	3.8±11.10	3.88±11.30
55-64	23.5±27.30	16.0±18.60	16.11±18.78
<65 (Derived)	32.7±33.84	19.8±21.66	19.99±21.92 *

Note: *The mean and STD of hypotension duration will be used in sample size estimation.

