2.4.3. Sample Size Estimate

Because there is no valid evidence available for the hemodynamic management from literature on intensive care unit, in this simulation only the information from closed chest stage and post cardiac pulmonary bypass stage are integrated.

By HPI CARE study objectives, clinical study design, and hypotheses test settings, a one side hypothesis test is the standard method, type I error for this test is 0.025, test power=0.80, control group mean hypotension duration=29 minutes, its stand deviation=29.49, the expected reduction is 30%, by the HPI arm result from non-cardiac clinical study, the ratio between hypotension duration STD and mean is around 1.10. The estimated subjects for each arm by 1:1 allocation is 142 from the simulation completed by SAS PROC POWER. Considered lost follow up, withdraw informed consent form, et al, 10% attrition will put on the estimated sample size. It is 157 subjects for HPI arm and control group.

Variable	Control Group (non-HPI arm)	Test Group (HPI Arm)
----------	--------------------------------	-------------------------

 Edwards	Revision Date: May 7, 2024	Rev	For Use Only by Affiliates of Edwards Lifesciences	Page 9
	Title	A randomized trial of the Hypotension Prediction Index in the cardiac operating room and the intensive care unit		

Mean hypo (minutes)	29 min	20.3 min
SD of Mean hypo minutes	29.49 min	22.33 min
Alpha (overall, one-sided)	0.025	---
Sides	One-Sided	---
Power	0.8	---
Sample size	142	142
Dropout rate	10%	10%
Sample size (subjects)	157	157

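### The protocol's base size of 171 per group does not follow from its own inputs, which give 142, and does not lead to 175; the SAP 2.4.3 table stops at 157 because it omits the interim uplift

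*Combined protocol and SAP*

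**What the plan says.** Protocol section 7, Sample Size Justification, sets out a comparison of two means. The control input is "hypotension mean=29 (minutes), standard deviation=29.4 (minutes", the expected reduction is 30%, the test-arm ratio of SD to mean is 1.10, and power is 0.80. The error rate is "By clinical study design, type I error $\alpha = 0.025$ (one side test"). It concludes that "with SAS PROC POWER, the estimate of sample size is 171 per group". Protocol section 7, Planned Interim Analyses, then adds 11% for the Pocock interim look and says that "another 10% attrition is added for subject enrollment; the final sample size is 175 subjects per group".

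SAP 2.4.3 uses the same inputs apart from a small change in the control SD: "control group mean hypotension duration=29 minutes, its stand deviation=29.49, the expected reduction is 30"%. Its result is different: "The estimated subjects for each arm by 1:1 allocation is 142 from the simulation completed by SAS PROC POWER". It adds 10% for attrition and ends there: "It is 157 subjects for HPI arm and control group". The table in SAP 2.4.3 stops at the same number and has no row for the interim look. SAP 8.1.4 adds 11 to 12% for the interim look and a further 10% for attrition, and states 175 per group.

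On the control SD, SAP Table 1 derives 21.92 for the post-bypass period, and its note says "The mean and STD of hypotension duration will be used in sample size estimation". SAP 2.4.2 says that this is combined with a closed-chest mean of 9 and SD of 15 minutes.

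**The concern.** Both documents credit SAS PROC POWER, on practically the same inputs, with two base sizes that differ by 29 per group. The larger one sits only 2.3% below the final 175 (175/171 = 1.023), although the protocol says that two uplifts of 11% and 10% lie between them. The SAP in turn reaches a final per-arm number in 2.4.3 that is not the one in 8.1.4.

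The base size, the uplifts and the final size are figures that the trial relies on. As written, a reader cannot reproduce the protocol's chain and cannot see in the SAP table that the interim look has been allowed for. The interim analysis is also timed at half of enrolment, so the target needs to be unambiguous: half of 2 x 175 is 175 subjects, and half of 2 x 157 is 157.

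**Working it through.** **Inputs.** Control mean 29 and SD 29.4 (protocol) or 29.49 (SAP 2.4.3). A 30% reduction gives a test mean of 0.70 x 29 = 20.3, so the difference is 8.7 minutes. Test SD = 1.10 x 20.3 = 22.33. One-sided alpha 0.025 (z = 1.960), power 0.80 (z = 0.842), 1:1 allocation.

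**Base size.** For two means with unequal SDs, n per group = (SD0² + SD1²)(z_alpha + z_power)² / difference², with (1.960 + 0.842)² = 7.849.

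- SAP: (869.66 + 498.63) x 7.849 / 75.69 = 141.9, so 142. The SAP's figure reproduces.
- Protocol: (864.36 + 498.63) x 7.849 / 75.69 = 141.3, so 142. The protocol's 171 does not reproduce.
- Exact (noncentral) t gives 143 with either SD.

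**Other readings of the protocol inputs (normal formula).**

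| Reading | n per group |
|---|---|
| Control SD 29.4 in both arms | 180 |
| Test SD 22.33 in both arms | 104 |
| Average of the two SDs | 139 |
| Pocock level 0.015, one-sided | 164 |
| Power 0.85 | 162 |

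None of these gives 171.

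**From base to final size.**

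| Start | Interim | Attrition x 1.10 | Attrition / 0.90 |
|---|---|---|---|
| 171 | x 1.11 = 189.8 | 208.8 | 210.9 |
| 142 | x 1.11 = 157.6 | 173.4 | 175.1 |
| 142 | x 1.12 = 159.0 | 174.9 | 176.7 |

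The 175 follows from 142 by either 142 x 1.11 / 0.90 or 142 x 1.12 x 1.10. It does not follow from 171. The 11% itself is right: the computed inflation for a two-look Pocock design at these settings is 1.110.

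**The SAP's 157.** 142 x 1.10 = 156.2, rounded up to 157. This is the base plus attrition only. It happens to lie next to 157.6, the size after the interim uplift and before attrition, but the two are different steps.

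**Power of the planned enrolment.** 175 x 0.90 = 157.5 evaluable per arm. With two equally spaced looks and a Pocock boundary of one-sided 0.0147 per look, 157 per arm gives 80.0% power at SD 29.4 and 79.9% at SD 29.49 (normal approximation).

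**Control SD.**

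- Table 1 adds the variances of the two pressure bands with no covariance: sqrt(11.30² + 18.78²) = 21.92.
- The same rule with the closed-chest SD gives sqrt(21.92² + 15²) = 26.56, not 29.49.
- Reaching 29.49 needs a correlation of (29.49² − 21.92² − 15²) / (2 x 21.92 x 15) = 0.25, which neither document states.

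**The case against.** The best defence is that nothing that matters in practice is wrong. The final size is 175 per arm in the protocol synopsis, in protocol section 7 and in SAP 8.1.4, and that size delivers the intended power. The SAP's 142, 157 and 175 are not rival answers: they are the base, the base plus attrition, and the size with both uplifts. SAP section 1 also says that the SAP prevails in a conflict on data analysis, which favours 142. All of this stands, except that sample size is only arguably data analysis. It narrows the point to one wrong base figure and one missing step, but it does not make 171 correct or the SAP table complete.

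Three stronger readings are tempting, and the documents do not support them.

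- A reader might infer that the one-sided alpha was halved, because one-sided 0.0125 gives 171.2. But 141.34 x 1.21, the base with both uplifts added together, gives 171.0 and fits at least as well. Neither origin is documented.
- A reader might infer from 175 against 171 that attrition and the interim look were left almost unfunded. That holds only if 171 is the true base, and the stated inputs show that it is not.
- A reader might infer that the trial is underpowered, on the ground that the two pressure bands are positively correlated and the control SD should therefore be larger. The documents give no such correlation. The rule that Table 1 does use, carried through to the closed-chest period, points the other way: SD 26.56 and about 85% power with 157 per arm.

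**Conclusion.** Wrong as written. The protocol's 171 is 29 above what its inputs give (142, or 143 by exact t), and with the stated uplifts it leads to 209 to 211 rather than 175. SAP 2.4.3 leaves out the interim uplift and so stops at 157, at odds with SAP 8.1.4. The control SD differs slightly between the documents (29.4 and 29.49), which does not change the rounded base size, and its derivation cannot be reproduced without an unstated correlation of about 0.25.

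The planned enrolment of 175 per group is not in question. It follows from 142 and gives about 80% power. That rests on the stated means and SDs, 10% attrition, and two equally spaced Pocock looks. Both documents acknowledge that these inputs come from operating-room data only.

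**What to change.** 1. In protocol section 7, replace 171 with 142.
2. In the text and table of SAP 2.4.3, add a step for the Pocock interim uplift, so that the chain runs 142, about 158 after the uplift, 175 after 10% attrition. Replacing 157 with 175 without that row would leave a table that does not compute.
3. State the same chain in both documents, with one interim percentage (the protocol has 11%, the SAP 11 to 12%), and say whether attrition is applied as x 1.10 or / 0.90.
4. Use one control SD, 29.4 or 29.49, in both documents, and state how it was combined from 21.92 and 15, including any correlation assumed.

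The cost is wording only. Enrolment stays at 175 per group and the analysis does not change.

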8. RISK ANALYSIS

Anticipated Risks

Edwards will monitor for safety which include those potentially associated with use of the devices and its components. There may be additional risks and discomforts that are not known at this time.

All trial devices are commercially available. Any events associated with any commercially available trial device will be reported in accordance with the Medical Device Reporting (Complaints) regulation (21 CFR Part 803).

Below is a list of general anticipated risks associated with the type of surgeries and procedures, which may be conducted as standard of care.

- Risks related to cardiopulmonary bypass surgery:
 - Death
 - Hemolysis
 - Capillary leak syndrome
 - Post-perfusion syndrome
 - Air embolism
 - Formation of blood clots
 - Acute respiratory distress syndrome
 - Systemic inflammatory response
 - Organ failure
 - Bleeding
- Risks related to other surgical or patient factors:
 - 30-day mortality
 - Cardiac arrest
 - Cardiac arrhythmia
 - Hemorrhage
 - Ileus
 - Nausea and vomiting
 - Pneumonia
 - Prolonged Hospital length of stay
 - Prolonged ICU length of stay
 - Pulmonary embolism
 - Sepsis
 - Transfusion need
 - Wound infection

THIS DOCUMENT CONTAINS CONFIDENTIAL AND PROPRIETARY INFORMATION OF EDWARDS LIFESCIENCES, LLC. IT MAY NOT BE REPRODUCED OR DISCLOSED WITHOUT PRIOR WRITTEN PERMISSION FROM EDWARDS LIFESCIENCES, LLC.

Edwards Lifesciences, Edwards, the stylized E logo, HemoSphere, Acumen IQ, Swan Ganz and ForeSight Elite are trademarks of Edwards Lifesciences Corporation.

Below is a list of anticipated risks that may be associated with the use of the Acumen IQ Sensor:

The vascular access obtained is standard clinical care for the adult population and the addition of the Acumen IQ sensor is not expected to impose any additional risk to the patient. There is no measurable increased infectious risk with the temporary use of the Acumen IQ sensor.

Below is a list of anticipated risks that may be associated with the use of ForeSight Elite Sensors:

- Allergic reaction to adhesive on sensors
- Skin irritation

In addition to the risks mentioned above, use of the HPI Pressure & Flow Optimization Protocol may lead to undertreatment or overtreatment with vasoactive drugs or fluids.

Under- or overtreatment may result in the following anticipated risks:

- Heart failure
- Profound hypotension
- Hypertension
- Cardiac ischemia
- Tachyarrhythmia
- Bradycardia

Risk Management

The trial devices have been tested to an established regimen of safety and performance testing and have been cleared by the US FDA in adults.

The current risks identified for using these products do not outweigh the benefit the patient will receive. Furthermore, this trial is:

- 1) Being conducted on patients who are already planned to receive an arterial line and the addition of Acumen IQ sensor do not add to the invasiveness of the trial. The optional use of the noninvasive ForeSight Elite sensors also does not add any additional risks. As such, the risks do not outweigh the benefits.

Benefits

There are no guaranteed benefits from a subject's participation in this trial.

9. REPORTABLE EVENTS

Recording and Reporting of Adverse Events

The Investigator and/or Designee(s) will determine whether any adverse events (AEs) have occurred. An AE is defined as any untoward medical occurrence in a clinical trial of a Trial Device regardless of the causal relationship of the problem with the device or, if applicable, other trial treatment or diagnostic product(s). Information for AEs with the trial devices will be collected from the time a subject begins the trial related procedure and/or is exposed to trial product(s). AEs will also be collected during surgical intervention, post intervention, discharge and through the follow-up. AEs may be volunteered by subjects, clinicians, elicited from questioning by Investigator and/or Designee(s), or collected via observation. When a device- or trial-related AE is suspected all available event information and will be provided to the Medical Reviewer.

Once an AE/SAE/UAE is confirmed as such, event, date of onset, severity, duration, treatment (if required), resolution (or ongoing), assessment of seriousness, relationship to trial procedure and relationship to device will be recorded on the appropriate eCRF or SAE Report Form and submitted as necessary by the Investigator and/or Designee(s). Any suspected AEs related to the devices or trial procedure must be reported to the Sponsor or Designee within 24 hours of first awareness of the event.

Classification of an AE

The following guidelines will be used to describe the severity of the AE:

- Mild – Event requires minimal or no treatment and do not interfere with the subject's daily activities.
- Moderate – Event results in a low level of inconvenience or concern with the therapeutic measures. Moderate events may cause some interference with functioning.
- Severe – Event interrupts a subject's usual daily activity and may require systemic drug therapy or other intervention.
- Serious – Serious events are usually potentially life-threatening or incapacitating. Of note, the term "severe" does not necessarily equate to "serious."

Relationship of an AE

The evaluation of relatedness must consider etiologies such as natural history of the underlying disease, concurrent illness, concomitant therapy, trial-related procedures, accidents, and other external factors. In a device trial, the trial product(s) must always be suspect.

Causality of relationship to the trial product(s) will be judged by the Investigator who examines and evaluates the subject based on temporal relationship and his/her clinical judgment. Causality of relationship will also be reviewed by the Investigator, and independently by the Medical Reviewer as follows:

Not related:

- An event is clearly not and cannot be related to the trial product(s), and/or evidence exists that the event is definitely related to another etiology. Note: Reporting of these events to the Sponsor or designee within 5 working days of first awareness of the event is not required unless the event was related to the Device or Trial.

Possibly Related:

- There is some evidence to suggest a causal relationship may exist; however, the event could have been produced by another cause (e.g., treatment, condition). Note: Reporting of these events to the Sponsor or designee within 5 working days of first awareness of the event is required.

Related:

- A relationship can be directly attributed to the use of the Device. Note: Reporting of these events to the Sponsor or designee within 24 hours of first awareness of the event is required.

Recording and Reporting of Adverse Device Effects

An adverse device effect (ADE) is defined as an AE related to the use of the medical devices in this trial. This definition includes AEs resulting from insufficient or inadequate instructions for use, deployment, implantation, installation or operation, or any malfunction of the investigation device. It also includes any AE resulting from use error or from intentional misuse of the Trial Device.

ADEs must be reported to the Sponsor or designee, within 24 hours of first awareness of the event. Notification should be done via email, fax, telephone, or direct communication followed by direct entry of AE/SAE data into the eCRF. In addition, the Trial site will report confirmed ADEs related to their IRB in accordance with the IRB's requirements. ADEs will also be reported to the FDA, as required.

Recording and Reporting of Serious Adverse Event

A serious adverse event (SAE) is defined as an AE that results in any of the following outcomes: death, a life-threatening adverse event, inpatient hospitalization, or prolongation of existing hospitalization, a persistent or significant disability/incapacity, or a congenital anomaly/birth defect.

Recording and Reporting of Serious Adverse Device Effects

A serious adverse device effect (SADE) is an ADE that has resulted in any of the consequences or characteristics of a SAE.

SADEs must be reported to the Sponsor or designee, within 24 hours of first awareness of the event. Notification should be done via email, fax, telephone, or direct communication followed by direct entry of AE/SAE data into the eCRF. In addition, the Trial site will report confirmed SADEs their IRB in accordance with the IRB's requirements. SADEs will also be reported to the FDA, as required.

Recording and Reporting of Unanticipated Adverse Device Events

Unanticipated adverse device effect (UADE) is defined in 21 CFR 812.3(s) as any serious adverse effect on health or safety or any life-threatening problem or death caused by, or associated with, a device, if that effect, problem, or death was not previously identified in nature, severity, or degree of incidence in the investigational plan or application (including supplementary plan or application), or any other unanticipated serious problem associated with a device that relates to the rights, safety, or welfare of subjects. In contrast, an anticipated adverse device effect is an effect which by its nature, incidence, severity, or outcome has been identified in the risk analysis report.

UADEs must be reported to the Sponsor or designee within 24 hours and submitted to the reviewing IRB as soon as possible, but in no event later than 10 working days after the Investigator first learns of the effect. All AEs related to the Device or Trial will be reviewed by the Investigator and/or Designee(s) and Sponsor. These AEs will be followed until they are adequately resolved, explained by the Investigator and/or Designee(s), until subject has completed follow-up, terminated the Trial early, is lost to follow-up or has been withdrawn from the Trial.

Recording and Reporting of Deaths

Events resulting in death during the subject's enrollment in this Trial are not expected to occur as a result of participation in the Trial. In the event of subject death; however, every reasonable effort should be made to obtain a copy of the autopsy report and/or death summary. Information on the date and cause of death and its relationship to the trial device will be determined by the Investigator and/or Designee and recorded on the appropriate AE eCRF and submitted on an SAE Report Form as necessary.

Recording and Reporting of Adverse Events Associated with Commercial Components

Any adverse event associated with an FDA cleared component will be recorded as a device complaint and reported via the MDR program (21 CFR Part 803). Complaints will also be reported to the IRB in accordance with each IRB's requirements. Device complaints should be reported to the Sponsor as soon as the site becomes aware of the complaint. The Sponsor may request further information and documentation from the site when complications and/or malfunctions are observed and reported.

Recording and Reporting of Pre-Existing Conditions

Pre-existing medical conditions and symptoms due to pre-existing medical conditions, surgery or admission to ICU will not be recorded as adverse events. The admission of a critically ill patient in the intensive care unit is commonly due to one or several serious medical conditions and/or a major surgery, which may cause changes and abnormalities of blood chemistry, diagnostic and physiological parameters. In the event there is a deterioration of a pre-existing medical condition or symptoms due to the use of the Trial product(s) or a Trial related procedure, then the review of the event will be initiated, and an AE will be recorded if it meets the definition. Any events occurring prior to the exposure to the Trial product(s) or Trial related procedure will be recorded as medical history.

Reporting Adverse Events to the FDA

Confirmed UADEs will be evaluated by the Clinical Events Committee. The FDA, all participating principal investigators and their reviewing IRBs will be informed no later than 10 working days after Edwards Lifesciences or designee first becomes aware of the effect.

Reporting Adverse Events to the Responsible IRB

In accordance with applicable policies of the IRB, the Investigator will report, any observed or volunteered confirmed adverse event that is determined to be (1) unexpected; (2) related or possibly related to the research; and/or (3) involves increased or greater risk of harm to participant(s) or others than was previously known or approved by the IRB. AE reports will be submitted to the IRB in accordance with the IRB policies and procedures.

Confirmed UADEs will be evaluated, and the reviewing IRB will be informed of the results of the Trial no later than 10 working days after Edwards or when the designee first becomes aware of the effect.

Recording and Reporting AE Time Period

At each Trial visit, the Investigator and/or Designee(s) will inquire about the occurrence of AE/SAEs/ADEs/SADEs/UADEs since the last visit. AE/SAEs/ADEs/SADEs/UADEs will be followed until they are adequately resolved, explained by the Investigator and/or Designee(s), until subject has completed follow-up, terminated the Trial early, is lost to follow-up or has been withdrawn from the Trial.

